8.4.1. ADVERSE EVENT REPORTING

The investigator must document all AEs on the AE Source Documents and subsequently enter this information into the electronic case report form, which will be reviewed by the study monitor and provided to the study sponsor. AE source documentation must be signed off by the procedure-trained investigator.

8.4.2. SERIOUS ADVERSE EVENT REPORTING

The study investigator must report all SAEs and SADEs to the study sponsor immediately and without delay within 24 hours of site awareness and complete a AE CRF. See Section 1, clinical monitoring, for primary contact information.

All SAEs and SADEs will be followed until satisfactory resolution or until the site PI deems the event to be chronic or the adherence to be stable. Other supporting documentation of the event may be requested by the study sponsor and should be provided as soon as possible.

The study sponsor will be responsible for notifying FDA of SAEs pursuant to the MDR reporting requirements (21 CFR 803.19(a)(2)).

8.4.3. UNANTICIPATED PROBLEM REPORTING

An investigator shall submit to the sponsor and to the reviewing IRB a report of any Unanticipated Adverse Device Effect (UADE) occurring during an investigation as soon as possible, but no later than ten (10) working days after the investigator first learns of the effect (21 CFR 812.150(a)(1)).

A sponsor who conducts an evaluation of an unanticipated adverse device effect under 812.46(b) shall report the results of such evaluation to FDA pursuant to the MDR regulations and to all reviewing IRB's and participating investigators within tent (10) working days after the sponsor first receives notice of the effect.

8.5. STUDY HALTING RULES

Circumstances that may warrant termination or suspension include, but are not limited to the following unlikely events:

- Determination of unexpected, significant, or unacceptable risk to participants
- Insufficient compliance to protocol
- Determination that it is unlikely that the study null hypothesis can be rejected

8.6. SAFETY OVERSIGHT

Adverse events will be reviewed periodically by the Medical Monitor. For any reported SAE, the Medical Monitor and Scientific Advisory Board members will review the relevant materials and may issue a recommendation to terminate the study as described above.

If this recommendation is reached, then the PI, study sites and IRBs will be notified. In addition, Spirox will follow the MDR reporting requirements pursuant to (21 CFR 803.19(a)(2)).

Spirox Latera™ implant support of lateral wall cartilage (LATERAL-OR) study SPI-CP-301

9. CLINICAL MONTIORING

Clinical monitoring and oversight of the study will be conducted by Spirox, to ensure that the safety, rights and well-being of human subjects are protected, that the reported trial data are accurate, complete, and verifiable, and that the conduct of the trial is in compliance with the currently approved protocol/amendment(s), with GCP, and with applicable regulatory requirement(s).

The clinical site monitoring plan for this study will utilize both on-site and centralized (remote) monitoring, with on-site visits occurring early in site enrollment and continuing throughout the study as deemed necessary. Data verification will consist of 100% Source Document Verification of primary and secondary endpoint data and adverse device effects through 6 months, verification of correct ICF execution, subject eligibility, and compliance with the protocol. Clinical monitoring for the remainder of the data collected includes CRF reviews for timing, completeness and consistency of the CRF data for each subject through study exit. Onsite visits are documented including letters to the site principal investigator for visit planning and for a summary of any visit observations.

An independent audit of Clinical Study File at Sponsor's site may be conducted during the course of the study.

10. STATISTICAL CONSIDERATIONS

10.1. STATISTICAL AND ANALYTICAL PLANS

A Statistical Analysis Plan (SAP) will be finalized prior to database lock, which will contain further analysis details and statistical methods.

10.2. STATISTICAL HYPOTHESES

Primary Efficacy Endpoint:

• The primary efficacy endpoint is the proportion of treatment responders at 6 months post procedure. Since there is no direct comparison group in this study, the primary efficacy hypothesis is a superiority comparison to a target proportion:

Null Hypothesis H₀: the proportion of responders at 6 months is = 0.50, versus Alternative Hypothesis H_A: the proportion of responders at 6 months is \neq 0.50

• There are no other formal statistical hypotheses.

10.3. ANALYSES DATASETS

Three analysis populations will be considered:

- Intention-to-Treat (ITT) Population: all enrolled subjects who began a nasal Implant procedure
- Modified Intention-to-Treat (mITT) Population: all subjects enrolled who received at least one nasal Implant
- Per-Protocol (PP) 6 Month Evaluable Population: subjects with 6 month post-Implant NOSE score assessments in clinic or by telephone

10.4. DESCRIPTION OF STATISTICAL METHODS

10.4.1. GENERAL APPROACH

This is a prospective, single arm, open label controlled study to evaluate the impact of Spirox Latera[™] alone or in conjunction with other procedures over 24 months of follow-up. Each patient will serve as his or her own control.

The study reference day (Day 1) is the day of the Implant procedure.

"Baseline" NOSE score refers to the measurement taken prior to the start of the procedure during the baseline visit.

Continuous variables will be summarized with descriptive statistics (N, mean, SD, median, quartiles), and categorical variables will be summarized as N (%).

Unless otherwise indicated, all p-values and confidence intervals will be 2-sided.

10.4.2. ANALYSIS OF THE PRIMARY EFFICACY ENDPOINT(S)

The primary endpoint will be the proportion of treatment responders at 6 months post procedure.

Responder is defined as subject that has at least one (1) NOSE class improvement or at least 20% NOSE score reduction

Subjects will be classified as non-responders if neither of these criteria is met.

NOSE score is a patient-reported outcome instrument which measures the impact of nasal obstruction on quality of life. It is scored in increments of 5 points, and the total score is calculated as the sum of all 5 questions multiplied by 5, where the range is 0 (asymptomatic) to 100 (most extreme deleterious impact on quality of life). The NOSE score classes¹⁶ are based on the total calculated score:

Mild: 5 – 25 points Moderate: 30 – 50 points Severe: 55 – 75 points Extreme: 80 – 100 points

This primary hypothesis will be evaluated for the 6 Month Evaluable Population using a -2-sided exact test²³, and the corresponding exact (Clopper-Pearson) 2-sided 95% confidence interval will be calculated. The null hypothesis that the proportion of responders is \neq 0.5 will be rejected if the p-value is < 0.05.

Sensitivity analyses will be conducted to determine the impact of missing data on these results. These analyses will depend on the extent of missing data, and will be detailed in the SAP, but may include:

- 1. Last observation carried forward (LOCF)
- 2. Subjects with missing data classified as non-responders

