7.1.4. Follow-Up Evaluation Visits (Visit 4-9)

Safety and performance data will be collected at 1 month (+/- 7 days), 3 months (+/-15 days), 6 months (+/- 15 days) 12 months (+/- 30 days), 18 months (+/- 30 days) and 24 months (+/- 30 days) post procedure.

A detailed description of the visit assessments and evaluations are located in Section 7.2. The following data will be collected:

- 1. NOSE scale (See Section 7.2.1)
- 2. NAO Breathing Assessment (See Section 7.2.2)
- 3. Subject Satisfaction Questionnaire (See Section 7.2.13)*
- 4. Post Procedure Health Economics Questionnaire (See Section 7.2.4)*
- 5. Update Concomitant Medications, if changed (See Section 8.9)
- 6. Adverse Events since last visit (See Section 8)
- 7. Post Procedure Nasal Exam (see section 7.2.7)*
- 8. Lateral Wall Motion Video 6 Month Visit only (See Section 7.2.9)*
- 9. Photography Cosmetic (select sites only) 3 and 6 Month Visits only (See Section 7.2.10)*
- 10. Photography 3D (select sites only) 3, 6 and 12Month Visits only (See Section 7.2.11)*

*This assessment/evaluation will not be collected at the 18 month and 24 month follow ups

Spirox Latera™ implant support of lateral wall cartilage (LATERAL-OR) study	Version 2.0
SPI-CP-301	September 7, 2017

Adverse events observed through the 12 month visit will be collected and documented. Only adverse device effects will be collected beyond the 12 month visit. Spirox will be notified as necessary pursuant to the description provided in Section 8. Data collected for these visits should be entered into the EDC no later than seven (7) days after the completion of each visit.

Upon completion of the follow-up visit activities, the subject will be scheduled for the next Follow-up Evaluation Visit.

Subject participation will be complete at the 24 month follow-up time point and documented in the Study Exit eCRF.

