7.6. PROHIBITED MEDICATIONS, TREATMENTS, AND PROCEDURES

Concomitant medications or therapies preventing subjects from being eligible to participate in this study are current use of nasal oxygen, CPAP, chronic use of systemic steroids and/or recreational intra-nasal drugs. Additionally, concomitant radiation exposure in the treatment area or chemotherapy will deem a subject ineligible to participate.

In addition, according to the study protocol, the following treatments are not permitted concurrent with index procedure or within 24 months after index procedure:

- Functional Endoscopic Sinus Surgery (FESS)
- Sinuplasty procedure
- Rhinoplasty procedure
- Any surgical or non-surgical treatment of the nasal valve, other than the index procedure, within 12 months of the study
- Use of a dilator and/or an external device in the nasal area (e.g. nasal strips).

Spirox Latera™ implant support of lateral wall cartilage (LATERAL-OR) study	Version 2.0
SPI-CP-301	September 7, 2017

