8. ASSESSMENT OF SAFETY

8.1. SPECIFICATION OF SAFETY PARAMETERS

All Serious Adverse Events (SAE), Adverse Device Effect (ADE) and Serious Adverse Device Effects (SADE) will be collected and documented through the end of subject participation in the study. In addition, all non-serious device and procedure-related Adverse Events (AE) and all non-serious head and neck, and/or respiratory related AEs will also be collected and documented.

The primary safety endpoint evaluation will consider nasal procedure related and Latera related adverse events through 6 months post-procedure.

The following information for each AE, ADE, SAE and SADE will be collected:

- Date of onset
- Status and/or Outcome
- Date of resolution
- Adverse Event/Effect type
- SAE or SADE
- Severity of event
- Relation to Study Device and/or procedure
- Action taken
- Descriptive narration of Event/Effect

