10.4.3. ANALYSIS OF THE SECONDARY ENDPOINT(S)

Response proportion as defined in section 10.4.2 will be evaluated for the 1, 3,6, 12, 18 and 24 month follow-up visits using the same technique as described for the primary endpoint.

Spirox Latera™ implant support of lateral wall cartilage (LATERAL-OR) study	Version 2.0
SPI-CP-301	September 7, 2017

Change in nasal airway obstruction from baseline at 1,3, 6, 12, 18 and 24 months post-procedure as reported by subjects on a VAS 0-100 mm scale (0= no difficulty breathing through nose; 100mm=not-able to breathe through nose) will be analyzed using a mixed model for repeated measures (MMRM). Least-square mean change from baseline and corresponding 95% confidence intervals will be reported. Baseline VAS score will be analyzed in a separate model, including decongestant use as a covariate. Decongestant use will be considered at baseline only to visualize the turbinate contribution to overall obstruction, thus no decongestant VAS will be assessed at the follow-up visits.

Results from the subject satisfaction questionnaire will be tabulated at 6 months. Sensitivity analyses for missing data will be described in the SAP.

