14.3. PROTOCOL DEVIATIONS

A protocol deviation is any noncompliance with the clinical trial protocol or GCP requirement. The noncompliance may be either on the part of the participant, the investigator, or the study site staff. As a result of deviations, corrective actions are to be developed by the site and implemented promptly.

These practices are consistent with ICH E6:

- 4.5 Compliance with Protocol, sections 4.5.1, 4.5.2, and 4.5.3
- 5.1 Quality Assurance and Quality Control, section 5.1.1
- 5.20 Noncompliance, sections 5.20.1, and 5.20.2.

It is the responsibility of the site to use continuous vigilance to identify and report significant deviations of identification of the protocol deviation to the study Sponsor. All deviations must be documented on a protocol deviation eCRF. Protocol deviations must be sent to the local IRB per the IRB's reporting requirements. The site PI/study staff is responsible for knowing and adhering to their IRB requirements.

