# 2.2.1. ANALYSIS SETS FOR EFFICACY AND SAFETY

The ITT analysis set will primarily be used for safety evaluations and will include all subjects who begin the implant procedure. Subjects who are consented but do not begin the implant procedure will not be included in the ITT analysis set. Because this is a singlearm, open-label study, the exclusion of subjects who do not begin the implant procedure is unlikely to result in biased response estimates. Subjects who begin the implant procedure but do not successfully receive an implant will be included in the ITT analysis set.

The mITT analysis set will consist of all subjects who successfully receive at least 1 Spirox LateraTM implant. Analyses supporting the primary and major secondary endpoints will, to the extent possible, be based on the mITT analysis set. Safety evaluations for events within 7 days of the implant procedure will be based on the ITT analysis set, and cumulative adverse events at 6 months will be based on the mITT analysis set. An important subgroup of the mITT analysis set is the 6 Month Evaluable (6ME) Set, which includes subjects with 6 month post-implant NOSE score assessments in clinic or by telephone.

The per-protocol (PP) analysis set will consist of all mITT subjects who have no major protocol deviations or events that might impact NOSE scores. These deviations may include changes to background nasal medications, prohibited medications and additional procedures prohibited by the protocol.

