#### SUPPORTIVE AND SENSITIVITY ANALYSES 4.2.2.1.

The primary endpoint analysis will be repeated using the PP analysis set. In order to quantify the impact of missing data on the primary analysis results, missing data may be imputed using 2 techniques:

- Last observation carried forward (LOCF) 1.
- Subjects with missing data classified as non-responders 2.

Since the efficacy of the device may deteriorate over time, LOCF represents the least conservative imputation technique, while classifying subjects with missing data as nonresponders represents the most conservative technique. These two analyses are reasonable upper and lower bounds for the response result, accounting for the missing data.

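### In the main 18 and 24 month responder rates, improvement after further nasal surgery counts as response; the SAP handles such surgery only by per-protocol exclusion, never as non-response.

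*Protocol*

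**What the plan says.** **Responder rule.** Protocol 10.4.2 and SAP 4.2.1 define response by NOSE class or percentage change and add only: "Subjects will be classified as non-responders if neither of these criteria is met". Protocol 10.4.3 extends the rule: "Response proportion as defined in section 10.4.2 will be evaluated for the 1, 3,6, 12, 18 and 24 month follow-up visits". Neither document gives later surgery a role in the classification.

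**Sensitivity analyses.** SAP 4.2.2.1 says "missing data may be imputed using 2 techniques", namely LOCF and missing counted as non-response. It also repeats the primary analysis in the PP set, which SAP 2.2.1 defines as "all mITT subjects who have no major protocol deviations or events that might impact NOSE scores", giving prohibited additional procedures as an example. SAP 3.6 links the PP exclusions to the primary and major secondary endpoints, and SAP 4 says the efficacy analyses will be repeated in PP.

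**Later procedures.** Protocol 7.6 states that "the following treatments are not permitted concurrent with index procedure or within 24 months after index procedure" and lists FESS, sinuplasty, rhinoplasty, nasal valve treatment and dilators. The nasal valve item has its own 12-month limit. Septoplasty and turbinate reduction are not listed. For listed procedures, 14.3 applies: "All deviations must be documented on a protocol deviation eCRF".

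**Collection after month 12.** Protocol 7.1.4 says "Only adverse device effects will be collected beyond the 12 month visit". Protocol 8.1 says SAEs and device effects "will be collected and documented through the end of subject participation in the study".

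**Exit.** Protocol 5.4 lets the investigator withdraw a subject for safety or a prohibiting medical condition. No rule requires exit after further nasal surgery.

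**The concern.** Further surgery for obstruction may mean that the index treatment was not enough, or did not last. If the subject then improves and stays in the study, the NOSE-only rule credits that improvement to the index procedure.

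This matters most at months 18 and 24. The implant absorbs over about 18 months (Protocol 6.2), so these rates are the durability evidence. In the prior study, 3 of 30 subjects had other nasal surgery, all after the 12-month visit (Protocol 2.2). The risk is to how the reported rates are read. No formal test is at stake, because these endpoints carry no hypothesis (Protocol 10.2, 10.4.9).

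**Working it through.** **1. The plan's own figure.** With n = 150, the two-sided exact test of 0.50 rejects from 88 responders (p = 0.041); 87 does not reject (p = 0.060). Power at 66% is 97.5%, so the claim of more than 90% holds. The sample size is not in question. The design rate gives 0.66 × 150 = 99 responders, and 99 − 87 = 12. Twelve responders would have to be recoded for the month 6 result to be lost. The prior study reported no other nasal surgery by month 6: 0/30, exact 95% upper limit 11.6%. Thirty subjects cannot exclude a few cases, but nothing in the documents points to early re-operation.

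**2. How each analysis treats a re-operated subject who stays and improves.**

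| Analysis | Treatment |
|---|---|
| Main responder rate | Responder |
| LOCF | No effect; a score is present |
| Missing as non-responder | No effect; a score is present |
| SAP PP repeat | Removed, if the surgery is known and judged excluding |
| Counted as non-responder | Not planned |

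**3. Possible size.** Shift = prior share × f × q × r. Here f is the share of this trial's subjects at the prior study's risk, q the share of re-operated subjects who would otherwise be non-responders, and r the share who respond after surgery. All three are assumptions. The prior shares are 2/30 = 6.7% by month 18 (exact 95% CI 0.8% to 22.1%) and 3/30 = 10.0% in all (2.1% to 26.5%). These come from implant-alone treatment, with surgery type not given.

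| Assumption | Month 18 | Month 24 |
|---|---|---|
| f = 11%, q = r = 100% | 2/30 × 0.11 = 0.7 points | 3/30 × 0.11 = 1.1 points |
| f = 50%, q = 50%, r = 80% | 2/30 × 0.20 = 1.3 | 3/30 × 0.20 = 2.0 |
| f = q = r = 100% | 6.7 | 10.0 |

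The 11% is the stand-alone share in commercial use (Protocol Appendix II). The last row is the most the observed shares can give, but it is not a ceiling: the upper confidence limits are higher, only 15 of 30 subjects completed 18 months, and the prior study had no 24-month visit. For scale, the exact 95% CI at 99/150 is 57.8% to 73.5%, a half-width of about 8 points.

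**4. What PP exclusion recovers.** Let N subjects include k re-operated, of whom s respond, and let R of the others respond. As observed: (R + s)/N. PP: R/(N − k). Counted as failures: R/N.

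- N = 150, k = 15, s = 12, R = 99: 111/150 = 74.0%; 99/135 = 73.3%; 99/150 = 66.0%. PP closes 0.7 of the 8.0 points.
- N = 150, k = 2, s = 2, R = 99: 101/150 = 67.3%; 99/148 = 66.9%; 99/150 = 66.0%. PP closes 0.4 of 1.3 points.

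The first case takes the full 3/30 share and is illustrative. PP is above the failure-coded rate whenever k and R exceed zero, because it removes failures from the denominator too.

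**5. Whether PP will catch the surgery.** SAP 2.2.1 says only that excluding deviations may include prohibited procedures, SAP 3.6 does not itemise surgery, and SAP 4.2.2.1 names PP only for the primary endpoint. Protocol 10.3 gives the PP label to the 6-month evaluable subjects, which excludes nobody for surgery. After month 12 the schedule in Protocol 7.7 lists NOSE, VAS, device effects and the exit form; the nasal exam, health economics questionnaire and general AE assessment stop. Contact may be by telephone or mailed form (5.3). An elective outpatient septoplasty or turbinate reduction could go unrecorded. The eCRFs are not in the documents, so this rests on the schedule.

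**The case against.** A reader might infer that no sensitivity analysis addresses later surgery. The documents do not support that. SAP 2.2.1, 3.6 and 4 together plan a PP repeat that reaches the major secondary endpoints, and the clause on events that might affect NOSE is wide enough to cover septoplasty or turbinate reduction.

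A reader might also infer that surgery after month 12 is not recorded at all. That too goes beyond the text. Protocol 8.1 keeps SAEs to the end of participation and also collects related and head and neck AEs. Protocol 8.3 asks about AEs at each visit, and rhinoplasty needs a deviation form. What stands is that 7.1.4 and 7.7 narrow this for months 18 and 24, and nothing asks directly about surgery.

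Two further objections have force. First, failure coding has its own bias: sinus surgery, cosmetic rhinoplasty or trauma repair is not a failure of the index treatment. The proposed rule should therefore be limited to surgery for obstruction. Second, the inflation needs the subject to stay. In the prior study all three such subjects exited, and if that happens here the later score is missing and this inflation does not arise. But this protocol leaves exit to the investigator.

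**Conclusion.** The point holds in a limited form. Later nasal surgery is handled only by PP exclusion, no planned analysis counts it as non-response, and the main 18 and 24 month rates count a retained, re-operated, improved subject as a responder. PP corrects only part of this, and only for recorded surgery.

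The size is unknown: about 1 to 2 points under moderate assumptions, and more if re-operation is as common as 3/30 and most such subjects stay and improve. A reader might take the 6.7 and 10.0 point figures as an expected bias. They are not; they need f, q and r all at 100%. Nor is the month 6 test under threat: it is unaffected in practice, and no change to it is proposed. Severity is minor to moderate: a cheap improvement to supportive endpoints.

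**What to change.** - Add to SAP 4.2.2.1 or 4.4.2 one sensitivity analysis of the 18 and 24 month responder rates. Count a subject with later surgery for nasal obstruction (septoplasty, turbinate reduction, rhinoplasty or a nasal valve procedure) as a non-responder from the surgery date. Do not count unrelated surgery, such as cosmetic or trauma repair.
- Report the number and type of operations by visit.
- Add one dated question on nasal surgery since the index procedure (type, reason, date) to the month 18 and 24 contact, including the telephone and mailed forms. Do this before those contacts finish, because unrecorded surgery is hard to recover later.
- Optionally, state in SAP 3.6 whether later nasal surgery is a PP exclusion, so that it agrees with SAP 2.2.1.

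The cost is one SAP paragraph, one form item with IRB review (Protocol 13.2), and a possibly lower rate in the sensitivity analysis. The primary analysis does not change.
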